8.2.2. Permitted Concomitant Therapy

8.2.2.1. COPD Medications and Non-Drug Therapies

To be eligible to be randomized in this trial, participants must present with an acute COPD exacerbation characterized by an eosinophilic phenotype and required systemic corticosteroids as SoC treatment in the urgent healthcare setting for the acute exacerbation. SoC for the index acute exacerbation is defined for this protocol as treatment with oral/systemic corticosteroid[s] (40 mg/day prednisone or equivalent) for 5 days with or without antibiotic(s) for 7 days; the modification of the dose and/or duration of prednisone (40 mg/day or equivalent) and/or the antibiotic is not recommended but may be allowed according to the Investigator's/medically qualified designee's judgement.

The start of SoC is defined as the start of either oral or systemic corticosteroids(s) or antibiotic(s), whichever is earliest.

Note: SoC must be documented in the participant's source documentation and in the eCRF. The use of other medications for treatment of the index acute COPD exacerbation and any subsequent COPD exacerbation(s), if applicable, is at the discretion of the Investigator or medically qualified health care personnel. Use of medication for treatment of subsequent exacerbations does not need to follow the SoC requirements for the index acute exacerbation.

In addition, participants are instructed to continue their regular COPD maintenance treatments (eg, LAMAs, LABA/ICS combinations, LABA/LAMA combinations, or LABA/LAMA/ICS combinations) for the duration of the trial. However, participants must withhold the morning dose of usual scheduled COPD medications on the morning of the spirometry assessments, except when treatment is needed for an acute COPD exacerbation.

Note: Modification(s) of the dosing regimen for the regular COPD maintenance treatments is(are) permitted as deemed medically appropriate by the Investigator/medically qualified designee; the modifications will be recorded in source documents and eCRF.

Other concomitant COPD maintenance medications may be allowed at the discretion of the Investigator following consultation with the Sponsor Medical Monitor, with the exception of short-acting anticholinergics for use as rescue medication.

Oxygen for intermittent use or PRN therapy ≤ 15 hours per day is allowed. LTOT or nocturnal oxygen therapy required for >15 hours is excluded throughout the trial.

8.2.2.2. Non-COPD Medications and Non-Drug Therapies

All medications for other disorders are permitted (except those listed in Table 3) as long as the dose remains constant whenever possible, and their use would not be expected to affect the efficacy (especially lung function) or safety assessments. The use of a continuous positive airway pressure (CPAP) device is permitted during the trial, provided that this therapy was initiated prior to Screening and the participant is on a stable regimen. Participants that require acute use of CPAP cannot be enrolled. Use of this therapy is to be recorded in the source document and eCRF. Participation in the acute or maintenance phase of a Pulmonary Rehabilitation Program during the trial is permitted. Participation is to be recorded in the source document and eCRF.

8.2.2.3. Rescue Therapy

The trial site will supply each randomized participant with albuterol [salbutamol] metered dose inhaler (MDI) for use in performing the post-BD FEV₁ assessments and as rescue medication for use as needed throughout the trial for treatment of acute symptoms of COPD.

A participant may use a different short-acting β -agonist (SABA) inhaler other than that provided (eg, a different brand of albuterol/salbutamol/ levalbuterol that is distributed at Screening). All SABA inhaler dosing (puffs) must be recorded in the daily e-diary.

In addition, rescue use of albuterol (salbutamol) nebulized administered via nebulization is discouraged, except as urgent treatment during a COPD exacerbation. Occasions where SABA is administered via nebulization will be recorded separately from metered dose inhaler inhalations in the e-diary. Use of low dose ICS-formoterol as rescue medication is not allowed during the trial.

Although the use of rescue albuterol (salbutamol) medications is allowable at any time during the trial, its use should be delayed for at least 4 hours prior to completing the pre-BD spirometry

assessments, unless required for treatment of an acute exacerbation COPD. It is anticipated that participants who are randomized into the trial will receive albuterol as part of the routine treatment of the acute COPD exacerbation during Visit 1b and Visit 2. In this instance spirometry should be scheduled to coincide with this treatment to allow post-BD recordings to be measured.

8.3. Treatment Compliance

The date and time of the dose of IP administered to the participant will be recorded in the source documents. The dose of IP and trial participant identification will be confirmed at the time of dosing by a member of the trial site staff other than the person administering the IP.

8.4. Randomization and Blinding

8.4.1. Participant Assignment

At Screening (Visit 1a or 1b), all participants are assigned a unique sequential identification (ID) number by site personnel. The participant number is a 7-digit number consisting of a 2-digit country code, a 2-digit site identifier, and a sequential 3-digit participant number.

Following the Screening Period, eligible participants will be randomized to one of the 2 treatment arms.

8.4.2. Randomization

All participants meeting enrollment criteria will be randomized at baseline (Day 0) to receive treatment with either rademikibart 600 mg SC or volume-matched placebo.

As participants qualify for randomization, they will be assigned to treatment by the IRT System. The random treatment assignments will be done in a 1:1 ratio. Randomization will be stratified by severity of the index acute COPD exacerbation (requiring hospitalization or not [yes/no]) at Baseline, and smoking status at Baseline (current or former).

See Section 7.4 for details on screen failures.

8.4.3. Blinding and Unblinding

This is a double-blind trial; neither the participants nor the Investigator will be aware of the treatment assignment for the participants. Blinding will be maintained throughout the trial by the use of active and placebo treatment of similar appearance and volume-matched dosing.

All Sponsor staff or designee will remain blinded to the treatment allocation until after the trial database is locked with the following exceptions:

- The independent statistician preparing the randomization codes, providing data to the DMC, and conducting the unblinded IA.
- A limited number of the Sponsor's senior management team (independent of the clinical trial team) who will receive results from the IA.
- The staff of the Sponsor or designee responsible for packaging IP.

- The staff of the Sponsor or pharmacovigilance vendor responsible for assessment and reporting of a suspected unexpected serious adverse reaction (SUSAR).
- The staff of contract research organizations (CROs) involved in processing the PK samples.
- The quality assurance auditors, where necessary.

8.4.4. Emergency Unblinding

The IRT interactive web response system will provide access to unblinded participant treatment information in the case of a medical emergency. In case of emergency when the treatment information is required by the Investigator to ensure a participant's safety in managing a medical condition, the treatment may be unblinded at the site by using a code break module. Whenever possible, the Investigator should contact the Sponsor prior to unblinding.

In the case of any intentional or accidental unblinding, the Sponsor or designee must be notified immediately. Whenever a treatment sequence is prematurely unblinded, the reason, date and time of the unblinding, and the individual who broke the blind, must be documented.

9. INVESTIGATIONAL PRODUCT MATERIALS AND MANAGEMENT

9.1. Investigational Product

The rademikibart drug product is formulated as a liquid sterile solution at 150 mg/mL in 10 mM L histidine, 60 mM trehalose, and 100 mM NaCl with 0.02% polysorbate 80 at pH 6.2. It is provided as a colorless-to-pale yellow sterile solution at 150 mg/mL concentration in a 1 mL single-dose PFS that delivers 1.0 mL solution.

Placebo solution is identical in appearance and content to the active solution except for rademikibart.

All IPs (rademikibart and placebo) will be supplied as a sterile PFS with a pre-assembled needle safety device. Each PFS is intended for a single 1 mL dose (150 mg) administered subcutaneously.

The individual IP information is presented in [Table 4](#).

Table 4: Investigational Products

Intervention Name	Rademikibart	Placebo
Intervention Description	Novel anti IL-4R α human monoclonal antibody	Matched-volume placebo
Formulation	Injection	Injection
Unit Dose Strength(s)	150 mg in 1 mL	Matching volume
Dosage	600 mg (4mL) 4 injections	Matching volume 4 injections
Duration of Treatment	Single-dose administration	Single-dose administration
Route of Administration	Subcutaneous injection	Subcutaneous injection

9.2. Investigational Product Packaging and Labeling

The PFSs of IP are packaged in paper boxes with supportive custom inserts.

Clinical labeling and packaging for all studies are conducted under Good Manufacturing Practice (GMP) manufacturing conditions. Labels are printed in accordance with local law with approved label specifications and are 100% visually inspected by Quality Assurance. Blinding of kit contents is maintained by assigning kit numbers to each package which are printed on both the drug product and the package labels. Kit numbers are assigned according to a pre-defined randomization schedule which is maintained within an IRT system.

9.3. Investigational Product Storage

The rademikibart drug product and matching placebo solution are to be stored between 2°C to 8°C. The drug product is stable for at least 1 month at 30°C.

9.4. Investigational Product Preparation and Administration

Rademikibart is intended for SC administration. The trial is designed to evaluate the efficacy and safety of a single 600 mg SC dose of rademikibart (administered as 4 separate 150 mg injections) as adjunct therapy to standard therapy.

IP will be administered by a qualified healthcare professional (eg, physician, physician assistant, nurse practitioner, pharmacist or trial nurse) at the site. The anatomical location of the injection site must be recorded in the source documents and in the eCRF.

The person administering the dose will wipe the skin surface of the upper arm, anterior thigh, or abdomen with alcohol and allow to air dry. The skin will be pinched to isolate the SC tissue from the muscle. The needle will be inserted at a 45-degree angle approximately halfway into the SC tissue. The trial medication will be slowly injected (at least 5 second duration is recommended) into the SC tissue using gentle pressure. The area should not be massaged after injection.

As multiple injections are required for IP administration, each injection site should be separated by at least 3 cm. Administration of the dose will be recorded in eCRF.

In the case of any incorrect administration of IRT-assigned treatment, the Sponsor must be notified immediately (within 24 hours) after first knowledge. Further details on IP administration are provided in the Pharmacy Manual.

9.5. Investigational Product Accountability

The Investigator (or designee) is responsible for maintaining accurate accountability records of the IP throughout the clinical trial. Appropriately trained personnel will inventory the IPs received and will maintain records of disposition of the drugs, including dates, quantity, and use. The Investigator or designee must maintain adequate records of the IPs (ie, accountability or dispensing logs) throughout the clinical trial: distribution, including the date received, number and units received, and lot numbers, storage, dispensing, and return or destruction of all IP. All dispensing and accountability records will be available for Sponsor or designee review. IP accountability records will be reviewed and verified during on-site and remote monitoring visits. At the end of the trial, the Sponsor or designee will conduct a final reconciliation of all IP accountability records.

9.6. Investigational Product Handling and Disposal

Further guidance and information for the final disposition of unused IP is provided in the Pharmacy Manual.

10. ASSESSMENT OF EFFICACY

Efficacy will be assessed via evaluations of the treatment failure rate, subsequent acute COPD exacerbations, spirometry assessments, venous blood gas (VBG) analysis (only for the hospitalized participants), patient-reported outcomes (PROs), and healthcare resource utilization and economics per the SoA (Table 5). PRO assessments carried out at trial visits will be completed as the first assessment in the visit schedule before spirometry or any other trial procedure.

10.1. Treatment Failure

Treatment failure is defined as death due to any cause, (re)admission to a hospital for COPD, ED (re)visit or unscheduled medical visit for worsening of COPD symptoms, or the necessity to intensify pharmacologic treatment (including second course of systemic steroids for COPD exacerbation) within 28 days after randomization.

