
utilization in participants with COPD and an eosinophilic phenotype experiencing an acute COPD exacerbation.
	
• Time to ready-for-discharge in hospitalized participants based on clinical assessment.• Time to ready-for-discharge in hospitalized participants based on VBG results• Total number of COPD-related hospital-stay hours during the first 28 days after discharge from the index acute COPD exacerbation (may include more than 1 COPD-related admission to the hospital).• Total number of COPD-related hospital-stay hours during the 8-week trial period (may include more than 1 COPD-related admission to the hospital).• For hospitalized participants: Hospital readmission rate during the first 28 days after discharge from the index acute COPD exacerbation and during the 8-week trial period.• Total number of all-cause hospital-stay hours during the first 28 days after discharge from the index acute COPD exacerbation (may include more than 1 admission to the hospital).• Total number of all-cause hospital-stay hours during the 8-week trial period (may include more than 1 admission to the hospital).• Incidence and rate of unscheduled visits for urgent care primarily related to COPD symptoms.• Incidence and rate of unscheduled calls for urgent care primarily related to COPD symptoms.• ICU admission rate during the first 4-week trial period.• Invasive ventilation rate during the first 4-week trial period.
---	---

 To explore the effect of rademikibart compared with placebo as an adjunct to standard therapy on improvement in symptoms, usage of rescue medications, and health-related quality of life/PROs in participants with COPD and an eosinophilic phenotype experiencing an acute COPD exacerbation. 	
 CFB in Dyspnea NRS at scheduled timepoints. Total dose/use of systemic corticosteroids. Use of daily puffs of rescue medication. CFB in SGRQ total score compared to placebo at Weeks 4 and 8. Proportion of participants with SGRQ improvement ≥ 4 points at Week 4 and Week 8. CFB in CAT total score compared to placebo at Week 1, Week 4, and Week 8. Proportion of participants with a decrease from Baseline in CAT total score ≥ 2 at Week 1, Week 4, and Week 8. CFB in clinical respiratory symptoms of COPD using the Evaluating Respiratory Symptoms in COPD (E-RS: COPD) comprised in the EXACT-PRO tool during the Follow-up Period at Week 8.
---	---

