6. INVESTIGATIONAL PLAN

6.1. Trial Design

This is a Phase 2, randomized, double-blind, placebo-controlled, parallel-group, interventional trial in participants with an acute COPD exacerbation with type 2 inflammation in the urgent healthcare setting to compare rademikibart plus standard therapy to standard therapy (plus placebo). For the purposes of this trial, an urgent healthcare setting may include an ED, a hospital inpatient ward, or an urgent healthcare facility, or a clinic affiliated with or in close proximity to a hospital/ED/urgent care equipped to provide the level of care specified in this protocol.

The trial is designed to evaluate the efficacy and safety of a single 600 mg SC dose (administered as 4 separate 150 mg injections) of rademikibart as adjunct therapy to standard therapy in adult participants with COPD characterized by an eosinophilic phenotype (peripheral blood eosinophil count of ≥ 300 cells/ μ L at Screening Visit 1b or as part of the assessment of the index acute COPD exacerbation within 72 hours prior to Screening) who require urgent healthcare treatment for an acute COPD exacerbation.

This trial will screen participants through 2 different channels:

1. Participants who consent to participate in the trial while in a stable condition, and
2. Participants who consent to participate in the trial at an urgent healthcare visit for acute COPD exacerbation.

Participants who consent to participate through channel 1 will be contacted by telephone approximately every 4 weeks after Screening Visit 1a to collect any changes in concomitant medications and any SAEs. The participant should be reminded to contact the site if they are experiencing worsening symptoms, so the site can determine if they may be experiencing an exacerbation and may qualify for randomization into the trial.

Details on treatment assignment are presented in Section 6.3. A trial schema is provided in [Figure 1](#).

[figure not shown]
For participants who are hospitalized due to an acute COPD exacerbation at randomization (Day 0), inpatient or on-site follow-up will take place as outlined in the Schedule of Assessments (SoA; [Table 5](#)). On the day of discharge, FEV₁ measurements should be performed in the morning prior to discharge, including pre-BD and post-BD measurements.

For participants who are not hospitalized, on-site follow-up procedures will also follow the SoA ([Table 5](#)).

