6.3. Treatment Assignment

Participants will be randomized in a 1:1 ratio to 1 of the following double-blinded treatment groups, stratified by severity of the acute COPD exacerbation (requiring hospitalization or not [yes/no]) at baseline, and baseline smoking status [current or former]:

- **Rademikibart** 600 mg dose administered as 4 SC injections of 1 mL (150 mg) each.
- **Matching Placebo** administered as 4 SC injections of 1 mL each.

IP (rademikibart 600 mg SC or placebo SC) will be administered on Day 0 as per the SoA (Table 5).

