10.6.1. Time to Ready-for-Discharge in Hospitalized Participants

For hospitalized participants, Investigators or their designees will assess participants daily during the initial hospitalization against the pre-defined discharge criteria based on clinical assessment (eg, normalization of acidosis, symptoms returning to manageable levels). The time required to meet these criteria will be used to evaluate the speed of initial recovery from COPD exacerbation in hospitalized participants.

This assessment applies only to hospitalizations due to the initial COPD exacerbation and is not applicable to hospitalizations resulting from subsequent COPD exacerbations.

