- For participants who consent to participate in the trial during the urgent healthcare visit for an acute COPD exacerbation, Visit 1b should be completed immediately after providing written informed consent and verifying eligibility.

b The Screening Period after Screening Visit 1b is up to 48 hours. Any procedures completed as part of the assessment and treatment of the COPD exacerbation may be used for Screening (eg, hematology, clinical chemistry, urinalysis, β -hCG if applicable, spirometry, chest X-ray or CT, ECG). Note that the maximum combined number of chest X-rays and/or CT scans must not exceed 2 for screening.

c Randomization/Baseline Visit is defined as Day 0 (Visit 2). Screening Visit 1b and Day 0 (Visit 2) may be the same day or up to 48 hours apart. If Visit 1b and Day 0 (Visit 2) are the same day, then FeNO and post-BD spirometry do not need to be repeated. For ECG, complete physical exam, and height/weight the Visit 1b assessment will serve as Baseline. All assessments at Visit 2 (Day 0) are to be conducted pre-IP dose administration with the exception of the assessment of SC injection sites and post-IP administration vital sign measurements.

d Visit 3 and Visit 4 are for participants who are hospitalized for current acute COPD exacerbation. Hospitalized participants discharged from the hospital prior to Visit 3 or Visit 4, or participants that were not hospitalized, should return to the trial site or have a home health care visit for spirometry assessments at Visit 3 and Visit 4 when feasible.

e At Visit 7, participants will be contacted by telephone.

f Medical history includes COPD history, COPD exacerbation history, past and current medical conditions (including cardiovascular and cerebrovascular medical history, surgical history), and substance usage.

g Participants will be trained on home use of the e-diary at Visit 2 and throughout the trial on an as needed basis. Participants will complete the assessment of EXACT-PRO every evening, and Dyspnea NRS and usage of short-acting rescue medications via e-diary twice daily at home.

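### The primary endpoint does not except an index admission that follows randomization, so read literally a participant dosed just before an already decided admission counts as a treatment failure in either arm

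*Protocol*

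**What the plan says.** Protocol section 10.1, repeated in the synopsis, lists the failure events as "death due to any cause, (re)admission to a hospital for COPD, ED (re)visit or unscheduled medical visit for worsening of COPD symptoms", together with a need to intensify drug treatment. The window is 28 days and opens at randomization. The bracketed prefix means that a first admission counts as well as a repeat one.

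Four other provisions bear on who can be admitted after randomization:

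- Section 6.1 on setting: "an urgent healthcare setting may include an ED, a hospital inpatient ward, or an urgent healthcare facility, or a clinic affiliated with" or near a hospital, ED or urgent care site.
- Section 6.3 on randomization: "stratified by severity of the acute COPD exacerbation (requiring hospitalization or not [yes/no]) at baseline". The stratum records a need for hospitalization, not that the participant is already in a bed.
- Section 6.1 on follow-up, by contrast, refers to participants who are hospitalized at randomization on Day 0.
- Appendix A, Table 5, footnote c: "Screening Visit 1b and Day 0 (Visit 2) may be the same day or up to 48 hours apart".

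Elsewhere the protocol does separate the index stay. Table 2 in section 5 has the exploratory endpoint "Hospital readmission rate during the first 28 days after discharge from the index acute COPD exacerbation", and section 10.6.1 says of readiness for discharge: "This assessment applies only to hospitalizations due to the initial COPD exacerbation". Section 10.1 has no such rule.

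**The concern.** A participant is assessed in the ED, judged to need admission, stratified accordingly, randomized and injected there, and then moved to a ward. That participant has a hospital admission for COPD after randomization. Taken at its word, section 10.1 scores this as failure, although the decision to admit was made before treatment. Had the injection been given on the ward, the same course would not count.

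The outcome would then depend on where the site gives the injection. Such events carry no information about the drug. They raise the failure rate in both arms and narrow the difference. Stratifying by need for hospitalization does not remove the problem, because both kinds of participant sit in the same stratum. The only adjudication committee described (section 6.8) handles cardiovascular events, so about 50 sites would apply this sentence themselves. The same endpoint feeds the conditional power calculation at the interim analysis (sections 13.2 and 13.7).

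**Working it through.** **Reading the text**

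1. The clock starts at randomization, not at index discharge (10.1).
2. A first admission counts. The phrase about worsening symptoms attaches to the ED or unscheduled visit and not clearly to the admission (10.1).
3. Randomization and dosing before physical admission are permitted (6.1; Table 5, footnote c). Participants who consented while stable are sent to the ED or urgent clinic for Visit 1b (11.1).
4. No section excepts the index admission from the primary endpoint.

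**Inputs from section 13.2:** 22.5% vs 45%; two-sided 5%; 1:1 allocation; 160 randomized; 5% dropout, so 160 × 0.95 = 152 evaluable, or 76 per arm.

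**The plan's own figure.** For two proportions with pooled variance under the null,

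power = Φ{ [d√n − 1.96√(2p̄(1−p̄))] / √(p₁(1−p₁) + p₂(1−p₂)) }.

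With n = 76, d = 0.225 and p̄ = 0.3375: (1.9615 − 1.3107) / 0.6495 = 1.002, so power is 84.2%. The stated target of at least 80% is reproduced.

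**Effect of counted index admissions.** Let q be the share in each arm that fails only because of the index admission, with the planned rates in the rest. Then p′ = q + (1−q)p, and the difference is (1−q) × 22.5 points. The protocol gives no value for q, so the values below are assumptions.

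| q | Rademikibart | Placebo | Difference (points) | Power, 76 per arm |
|---|---|---|---|---|
| 0 | 22.50% | 45.00% | 22.50 | 84.2% |
| 2% | 24.05% | 46.10% | 22.05 | 81.9% |
| 5% | 26.38% | 47.75% | 21.38 | 78.5% |
| 10% | 30.25% | 50.50% | 20.25 | 72.5% |
| 20% | 38.00% | 56.00% | 18.00 | 60.6% |

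Worked line for q = 10%: 0.10 + 0.90 × 0.225 = 0.3025 and 0.10 + 0.90 × 0.45 = 0.505. Unstratified power falls below 80% at q of about 4%.

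**Stratified approximation.** The primary test is Cochran-Mantel-Haenszel, stratified in part by this same hospitalization factor (13.4.5). All affected participants are placed in the hospitalized stratum and smoking status is ignored. The result depends on two further assumptions, the size of that stratum and the fraction of it affected:

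- q = 5% (20% hospitalized, a quarter affected): 79.3%.
- q = 10% (40% hospitalized, a quarter affected): 73.7%; (20% hospitalized, half affected): 75.8%.
- q = 20% (40% hospitalized, half affected): 65.5%; (20% hospitalized, all affected): 75.3%.

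Stratification softens the loss, by more when the affected participants fill most of their stratum, but does not remove it.

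**Sample size to restore 80% (unstratified).** At q = 10%, 91 per arm: 182 / 0.95 gives 192 randomized. At q = 20%, 120 per arm: 240 / 0.95 gives 253. The re-estimation in section 13.2 may add at most 80, for a total of 240.

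**The case against.** A reader might infer that the protocol makes these participants failures from Day 0. It does not say so. That is the literal reading of a definition that can be taken another way: admission for those managed as outpatients, readmission for those hospitalized for the index event. The exploratory readmission endpoint and section 10.6.1 fit that second reading, and inclusion criterion 10 treats the index visit or hospitalization as a condition of entry. This stands as a reason to call the text unsettled. It does not settle it, because those rules belong to other endpoints and the primary definition does not refer to them.

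The affected group may also be small. Participants already on a ward at randomization cannot be affected. Eligibility needs local laboratory results and chest imaging, and up to 48 hours may pass between Visit 1b and Day 0, so many index admissions will come before dosing. Nothing in the protocol shows that dosing ahead of admission is common. This stands: at q = 2% power is still 81.9%.

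A reader might also infer that the trial is underpowered or at risk of a false positive. Neither follows. The sample size is correct on its own inputs. Counted index admissions leave the null intact if they are equally frequent in both arms. The re-estimation could also recover the loss at q = 10% (192 is below the 240 ceiling) though not at 20%, and an increase is not guaranteed.

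The statistical analysis plan, not seen here, may define the derivation. Sites nevertheless record events against the protocol, which states the endpoint in full.

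**Conclusion.** The concern holds in this form. The primary endpoint does not say whether an admission for the index exacerbation that follows randomization counts, and its literal wording counts it. Where the admission was decided before randomization, that scores a pre-treatment decision as failure in either arm and makes the result depend on where the injection is given.

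The harm is dilution and site dependence, not inflated type I error. Its size cannot be fixed from the protocol. It is slight if about 2% of participants are affected, takes unstratified power below the stated 80% at about 4%, and costs roughly 12 points at 10% (84.2% to 72.5%). These figures assume that q is equal in both arms, that every affected participant is counted as failed, and that the planned rates apply to the rest.

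**What to change.** In section 10.1 and the synopsis, add wording to this effect:

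- A hospital admission for the index exacerbation is not a treatment failure if the decision to admit was recorded before randomization (stratum requiring hospitalization: yes, supported by source data) and the admission is continuous with the index urgent healthcare visit, with no discharge home in between.
- After index discharge, any readmission for COPD counts.
- For participants recorded as not requiring hospitalization, any admission for COPD after randomization counts.

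The other failure components are unchanged. The continuity condition is needed: an exception resting on the stratum alone would excuse someone sent home and admitted days later for the same unresolved episode. Source support for the decision keeps a stratification entry error from becoming an outcome error.

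The cost is small. It takes one paragraph in two places, an eCRF field for the time of the admission decision, and an edit check against randomization time. The failure count falls by the number of such index admissions. Treatment and visits do not change.
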